10.1.2 Serious Adverse Events

A serious adverse event is any adverse event as defined above that meets at least one of the following serious criteria:

- is fatal
- is life threatening (places the patient at immediate risk of death)
- requires in-patient hospitalization or prolongation of existing hospitalization
- results in persistent or significant disability/incapacity
- is a congenital anomaly/birth defect
- is an "other medically important serious event" that does not meet any of the above criteria

A hospitalization meeting the regulatory definition for "serious" is any in-patient hospital admission that includes a minimum of an overnight stay in a health care facility.

"Other medically important serious events" refer to important medical events that may not be immediately life-threatening or result in death or hospitalization, but may jeopardize the patient or may require intervention to prevent one of the other outcomes listed in the definition above. Examples of such events could include allergic bronchospasm, convulsions, and blood dyscrasias, drug-induced liver injury, events that necessitate an emergency room visit, outpatient surgery, or other events that require other urgent intervention.

10.1.3 Other Safety Findings

Other Safety Findings (regardless of association with an adverse event) include:

- Medication errors, overdose/underdose, whether accidental or intentional, misuse, addiction, or abuse, involving an Amgen product,
- Use of an Amgen product while pregnant and/or breast feeding,
- Transmission of infectious agents,
- Reports of uses outside the terms for authorized use of the product including off-label use,
- Accidental or Occupational exposure,

Protocol Number: 20130193
Date: 12 October 2022
Page 36 of 62

Any lack or loss of intended effect of the product(s)

10.1.4 Product Complaints

Product Complaints include any written, electronic or oral communication that alleges deficiencies related to the identity, quality, durability, reliability, safety, effectiveness, or performance of a drug or device after it is released for distribution to market or clinic. This includes any drug(s) or device(s) provisioned and/or repackaged /modified by Amgen. Drug(s) or device(s) includes investigational product.

Product complaints of IMLYGIC will be collected.

10.2 Safety Collection, Recording and Submission to Amgen Requirements

The Investigator is responsible for ensuring that safety events (adverse events, serious adverse events, product complaints, and other safety findings) observed by the Investigator or reported by the patient that occur after signing of the ICF through 30 days after the last dose of IMLYGIC; in addition, safety events (adverse events and serious adverse events) related to IMLYGIC treatment (as deemed by the Investigator) occurring 30 days after the last dose of IMLYGIC through 5 years of follow-up are recorded in the patient's appropriate study documentation. Those safety events which are considered serious must be submitted as individual case safety reports to Amgen via the applicable Amgen Safety Reporting Form (paper or electronic form) within 1 business day of Investigator's awareness. Non-serious Adverse Events must be reported in an expeditious manner, not to exceed 15 calendar days of awareness.

Protocol Exempted Events

One of the objectives of the study is to monitor for long-term safety of IMLYGIC. Hence, adverse events and serious adverse events occurring 30 days after the last dose of IMLYGIC through 5 years after the first IMLYGIC dose and deemed related to IMLYGIC by the Investigator are monitored and reported during the long term follow-up as outlined in Section 10.1. Adverse events and serious adverse events not deemed related to IMLYGIC by the investigator, and products complaints as defined in Section 10.1.4, and other safety findings as defined in Section 10.1.3 such as medication errors, overdose/underdose, misuse, addiction, abuse, off-label use involving IMLYGIC are not monitored during the long term follow-up because IMLYGIC is not administered to patients enrolled during the long-term follow-up phase of the study. Therefore, these other safety events are only monitored and reported during treatment with IMLYGIC and up to the safety visit (ie, up to 30 days after the last dose of IMLYGIC). The pregnancy

Protocol Number: 20130193 Date: 12 October 2022

and lactation cases are monitored during treatment and through 3 months after the last dose of IMLYGIC.

If any of the exempted reportable events during the long-term follow-up have a fatal outcome, they should be considered a serious adverse event and must be collected and reported individually within 1 business day from when the Investigator first becomes aware of the event.

All safety information that is not specified in this section is to be collected and submitted to Amgen within the specified time frame.

Protocol-exempted events and reportable events that are suspected to be related to any Amgen medicinal product where there is no exposure to IMLYGIC should be spontaneously reported to Amgen within 1 business day of investigator/vendor awareness. A list of all Amgen medicinal products can be found in the following link: https://www.amgen.com/amgen-worldwide

To spontaneously report a reportable event to Amgen, refer to the following link to locate your Local Amgen contact information by country: https://www.ext.amgen.com/contact-us/product-inquiries

Additional details on what to collect and report to Amgen for the reportable event can be found in the following link: https://wwwext.amgen.com/products/global-patient-safety/adverse-event-reporting

Reportable events suspected to be related to any non-Amgen medicinal product should be reported to the local authority in line with the local country requirements.

If the EDC system is unavailable to the site staff to report the adverse event, the information is to be reported to Amgen via a paper Adverse Event Contingency Report Form within 1 business day of the Investigator's awareness for serious adverse events and within 15 calendar days for non-serious adverse events. For EDC studies where the first notification of an Adverse Event is reported to Amgen via the Adverse Event Contingency Report Form, the data must be entered into the EDC system when the system is again available.

See Appendix **B** for sample Safety Report Form(s) and Form for Postmarket Report of Suspected IMLYGIC Associated Adverse Event for HCP or Close Contact; Appendix **C** for Additional Safety Reporting Information regarding the adverse event grading scale used in this study; and Appendix **D** for sample Pregnancy and Lactation Notification Worksheets.

The Investigator may be asked to provide additional information for any event submitted, which may include a discharge summary or extracts from the medical record.

Page 37 of 62

Protocol Number: 20130193 Date: 12 October 2022

Information provided about the event must be consistent with information recorded on study CRFs where safety data may also be recorded (eg, Event CRF).

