 - Examples of signs and symptoms include **but not limited to**: pain, burning, or tingling in a blister around the mouth or genitals, fingers, ears, **or any part of the body close to or far from the injection site**; eye pain, light sensitivity, discharge from the eyes, or blurry vision; weakness in arms or legs; extreme drowsiness; mental confusion.
 - If a patient answers "yes", then the following information about the infection will be collected: signs and symptoms, dates, reporting and testing for virus identification, and antiherpetic treatment received.
- Record the following information about IMLYGIC received: dates, dose concentration, injection volume.
- ¹ Record dates and types of other anticancer therapy received (see "f" for the list of therapies).
- ^k Record the following information about antiherpetic therapy received: dates, type (eg, acyclovir, valacyclovir, famciclovir, docosanol), administration route (oral, intravenous, topical).

Protocol Number: 20130193
Date: 12 October 2022
Page 7 of 62

Adverse events and serious adverse events that occur after the patient has signed the informed consent form (ICF) through 30 days after the last dose of IMLYGIC will be recorded in the electronic case report form (eCRF). Adverse events should be assessed on an ongoing basis.

- ^m Safety events which are considered serious must be submitted as individual case safety reports to Amgen via the applicable Amgen Safety Reporting Form (paper or electronic form) within 1 business day of Investigator's awareness.
- ⁿ Adverse events and serious adverse events that occur more than 30 days after the last dose of IMLYGIC and deemed by the Investigator to be related to treatment with IMLYGIC. **Any fatal outcome during long term follow up should be reported as a serious adverse event.**
- ^o Product complaints that occur after the patient has signed the ICF through 30 days after the last dose of IMLYGIC.
- P Other safety findings include, for example, medication errors, exposure to IMLYGIC during pregnancy and breastfeeding, accidental exposure, that occur after the patient has signed the ICF through 30 days after the last dose of IMLYGIC.
- ^q Record the following information on survival status: date of contact, status (eg, alive or deceased), and date and cause of death (if applicable).

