Although no cases of confirmed symptomatic herpetic infection from IMLYGIC have been reported to date, a potential risk to the patient is the risk for primary infection during treatment and reactivation from latent state after treatment due to the viral nature of IMLYGIC. Furthermore, another possible risk recognized by both Amgen and regulatory authorities is the potential reactivation of latent wild-type HSV-1 by IMLYGIC (eg, febrile response to IMLYGIC) which would increase the rate of infection by wild-type HSV-1. Lastly, secondary transmission and infection to the patient's close contacts and health care providers (HCPs) is a recognized potential risk. To further characterize these potential risks, this postmarketing prospective cohort study will follow a cohort of patients for up to 5 years after the first dose of IMLYGIC and monitor for herpetic infection in patients and for viral transmission to close contacts and HCPs through the existing Postmarketing IMLYGIC Surveillance Program. This study is an FDA Post Marketing Requirement #1 (PMR #1) and is listed as category 3 measure according to the European Union Risk Management Plan.

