10. COLLECTION, RECORDING, AND REPORTING OF SAFETY INFORMATION AND PRODUCT COMPLAINTS

10.1 Definition of Reportable Events

10.1.1 Adverse Events

An adverse event is any untoward medical occurrence in a patient administered a pharmaceutical product(s) irrespective of a causal relationship with this treatment.

An adverse event can, therefore, be any unfavorable and unintended sign (including an abnormal laboratory finding, for example), symptom, or disease temporally associated

Amgen Proprietary - Confidential

Product: IMLYGIC®

Protocol Number: 20130193
Date: 12 October 2022
Page 35 of 62

with the use of a product(s), whether or not considered related to the product(s). The definition of an adverse event includes:

- Worsening of a pre-existing condition or underlying disease.
- Events associated with the discontinuation of the use of a product(s) (eg, appearance of new symptoms).

It is the Investigator's responsibility to evaluate whether an adverse event is related to an Amgen product prior to reporting the adverse event to Amgen.

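### More than 30 days after the last dose, a non-fatal herpetic infection called unrelated leaves adverse event collection, and no listed field records its seriousness, hospitalisation, grade or outcome

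*Protocol*

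**What the plan says.** Until 30 days past the last dose, all adverse events are recorded. After that the rule narrows. Protocol 10.2 (Protocol Exempted Events) says that events "and deemed related to IMLYGIC by the Investigator are monitored and reported during the long term follow-up", and that "Adverse events and serious adverse events not deemed related to IMLYGIC by the investigator" are not monitored. Table 1 footnote n has the same restriction: events "deemed by the Investigator to be related to treatment with IMLYGIC". The reason 10.2 gives is that the product is no longer being administered in that phase.

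Death is excepted. Footnote n says "Any fatal outcome during long term follow up should be reported as a serious adverse event", and 10.2 says "If any of the exempted reportable events during the long-term follow-up have a fatal outcome, they should be considered a serious adverse event".

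On causality, 10.1.1 makes it the investigator's duty to "evaluate whether an adverse event is related to an Amgen product prior to reporting the adverse event to Amgen". Under 10.2, serious events are due within 1 business day of awareness and non-serious events within 15 calendar days.

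Herpetic infection also has its own collection route, which runs throughout follow-up whatever the causality call. If a patient reports symptoms, footnote h collects "signs and symptoms, dates, reporting and testing for virus identification, and antiherpetic treatment received". Section 6.2 lists among the risks under study both reactivation of the product virus from latency after treatment and "potential reactivation of latent wild-type HSV-1 by IMLYGIC".

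**The concern.** The reason given for the exemption does not fit this risk. Late reactivation is, by the protocol's own account, something that may happen after dosing has stopped, and patients are followed for up to 5 years from the first dose with that in view. Yet in that period the investigator's causality judgement decides whether a herpetic infection enters adverse event collection at all.

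Wild-type HSV-1 infections are the most exposed, because an investigator has least reason to call them related. Whether the product can trigger them is one of the questions the study raises. The infections counted include ocular herpes, encephalitis and disseminated disease (8.3.2.1), where seriousness, hospital admission and recovery matter most to someone reading the results. If these items are not collected, no analysis plan can recover them.

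**Working it through.** This is mainly a matter of reading the collection rules together. The only arithmetic is the share of follow-up to which the related-only rule applies.

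**1. What is recorded for an enrolled patient's non-fatal herpetic infection more than 30 days after the last dose**

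| Item | Called related | Called unrelated |
|---|---|---|
| Symptoms, dates, testing, antiherpetic treatment (footnotes h, k) | yes | yes |
| qPCR result in the eCRF (8.2.5) | yes | yes |
| Counted in the DNA and wild-type incidence rates (8.3.2, 8.7.2.4) | yes, by test result | yes, by test result |
| Adverse event or serious adverse event record (10.2, footnote n) | yes | no |
| Seriousness, hospitalisation, grade, outcome | through that record | not listed in footnote h |

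By comparison, the Appendix B form for health care providers and close contacts asks for serious-criteria codes, start and end dates, and hospitalisation. On the face of the protocol, a contact's suspected lesion is documented more fully in these respects than a patient's own late infection judged unrelated.

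**2. Two endpoints that can disagree on one infection**

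The primary endpoint counts suspected infections with detectable product DNA (8.7.2.4.1), whatever the causality call. The post-treatment adverse event endpoint (8.3.2.2) counts events the physician attributes to the product. On the Appendix B contingency form, relationship is entered at the initial report. Nothing in 10.1.1, 10.2 or Appendix B requires it to be reconsidered when the laboratory result comes back. An infection called unrelated and later found DNA-positive can thus be in the first endpoint and missing from the second.

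**3. Share of person-time under the related-only rule**

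Inputs:
- 535 patient-years from about 300 patients (8.5).
- Median treatment of about 6 months in the trial setting (Study Design Schema note). It is used here as if it were a mean, which is an assumption.
- 30 days of full collection after the last dose (10.2).

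Anchor check on the plan's own figure: the probability of at least one event at 3 per 1000 patient-years is 1 − exp(−0.003 × 535) = 1 − exp(−1.605) = 0.799. This agrees with the stated 80%.

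Mean follow-up = 535 / 300 = 1.78 years. Share = 1 − (treatment duration + 30/365.25) / mean follow-up.

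- 6 months: 1 − (0.50 + 0.082) / 1.783 = 0.67
- 3 months: 1 − (0.25 + 0.082) / 1.783 = 0.81
- 12 months: 1 − (1.00 + 0.082) / 1.783 = 0.39

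If mean follow-up is 2.0 years, the 6-month case gives 1 − 0.582 / 2.0 = 0.71. Re-treatment phases are ignored; they would lower the share.

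**The case against.** The strongest reply is that this is a deliberate and internally consistent choice. The post-treatment adverse event endpoint is defined as attributed events only, and 10.2 matches it. Incidence rates rest on test results, so no stated incidence endpoint is harmed. Footnotes h and k keep symptoms, dates, testing, and the type and route of antiherpetic treatment, which convey some of the clinical gravity. All of that stands, and it limits the point to missing clinical detail and unreconciled causality.

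Four stronger readings are tempting, and the documents do not support them:

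- A reader might infer that seriousness and outcome of all late infections are lost. They are not. Fatal outcomes are reported whatever the causality, footnote q records cause of death, and infections called related are fully collected.
- A reader might infer that causality must be fixed before the qPCR result. No laboratory turnaround is given. The 1-day clock makes this likely for serious events, but 15 days for non-serious ones may let the result arrive.
- A reader might infer that a first impression of an ordinary cold sore is final. Nothing prevents a later change of mind; the gap is that none is required.
- A reader might multiply the 67% by the 0.003 × 535 = 1.6 expected DNA-detected infections, giving about 1.1, and call those lost. That would be every expected late infection at a constant rate, not those judged unrelated, and all would still count in the primary endpoint. Applying the 3% to 5% general-population figure for frequent oro-labial recurrences (8.9.1) to 300 patients gives 9 to 15, but it ignores deaths and the treatment period, and treats untested lesions as confirmed wild-type.

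Two passages might seem to close the gap. The line in 10.2 that all safety information not specified in the section is to be collected does not reach these events, because the section does specify them, as exempt. The Appendix B instructions mention serious events regardless of causal relationship, but first defer to the protocol on which events to report.

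**Conclusion.** The point holds in a limited form. For non-fatal herpetic infections in enrolled patients more than 30 days after the last dose that the investigator calls unrelated, the protocol requires no seriousness, hospitalisation, grade or outcome data and no causality review after the test result. The number of such infections cannot be derived from the documents and may be small. What can be stated is the exposure to the rule: about 67% of person-time, with a range of 39% to 81% for 12 down to 3 months of treatment, given mean follow-up of 1.78 years and a median used as a mean.

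The conclusion also assumes that the eCRF follows footnote h; the form itself is not shown and may hold more fields. The change is worth making because it is cheap, concerns the study's own target event, and cannot be made good at the analysis stage.

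**What to change.** State in 10.2 (Protocol Exempted Events) and in footnote n that suspected or confirmed herpetic infections in enrolled patients are not exempt. They would be recorded as adverse or serious adverse events, with seriousness, grade and outcome, to the end of follow-up regardless of causality. Alternatively, add seriousness, hospitalisation, grade and outcome to the items in footnote h. Either way, require the investigator to reassess causality when the qPCR or HSV-1 result is received.

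In 8.7.2.4.2, add a listing of post-treatment herpetic infections showing the qPCR or HSV-1 result beside the investigator's causality. Do not class every DNA-positive infection as related automatically. Section 6.2 describes DNA-positive lesion swabs in the phase 2 study that were all negative for infectivity, and the sample laboratory report in Appendix E warns against using the result as the only basis for a diagnosis.

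The cost is a protocol amendment, a small number of extra adverse event forms at contacts that already ask about herpetic symptoms, and one listing.
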